Note: Ocular laser procedures are not excluded
11. Macular atrophy in either eye due to anything other than AMD

Novartis

Confidential

Page 53

Amended Protocol Version No. 01 (Clean)

Protocol No. CCLG561X2201A

12. Concomitant treatment for AMD in either eye within 90 days of screening
Note: Concomitant use of vitamins/supplements is not excluded
13. Any periocular or IVT injections in either eye within 90 days of baseline
14. Any of the following abnormal vital signs at screening: temperature > 100.5° F (38° C); heart rate > 100 bpm; systolic blood pressure < 90 mmHg or > 160 mmHg, diastolic blood pressure > 95 mmHg.
Note: Out of range vital signs may be repeated once. If the values are still out of range the visit must be rescheduled. If out of range vitals are observed again and persistent at re-measurement, the subject must be disqualified from the study. Subjects may be rescreened when values have stabilized.
15. Uncontrolled ocular hypertension or glaucoma in the study eye (IOP > 25 mmHg despite current pharmacological or non-pharmacological treatment)
16. Participation in any interventional clinical trial within 12 weeks prior to screening
17. Any history of participation in interventional clinical trials involving gene therapy or extended release products, or any product with expected long term efficacy

5 Restrictions for study subjects

During recruitment, screening/informed consent review, and baseline visit, the subjects must be informed and reminded of the following restrictions:

In general, systemic medications are allowed; however, corticosteroids (ophthalmic or systemic) should only be used if necessary.

- For both eyes, topical ophthalmic corticosteroids are allowed, however, for the study eye, no IVT ophthalmic agents are allowed
- For the fellow eye, there is no restriction to the use of any topical or IVT ophthalmic agents, provided they are not investigational products

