³ SE: study eye

⁴ For all visits requiring an IVT injection, IOP MUST be measured before and after the injection in the study eye

⁵ For all visits requiring an IVT injection, dilated ophthalmoscopy MUST be performed before the injection and immediately after the injection in the study eye
 Corporate Confidential Information

⁸ To be done at select sites only, see MOP for additional details

⁹ Assessment at screening is for source documentation purposes only

¹⁰ Unscheduled visit assessments as needed and as determined by the investigator, imaging not required

Corporate Confidential Information

Novartis

Confidential

Page 65

Amended Protocol Version No. 01 (Clean)

Protocol No. CCLG561X2201A

Table 8-3 Post-injection exams at injection visits

Visit	BL / V1					All injection visits									
Day	D1														
Injection	Inj 1														
Time point															
		Pre-Injection	Immediately Post-Inj	30 minutes Post-Inj	60 minutes Post-Inj, if required	Q 30 minute interval, if required	Pre-Injection	Immediately Post-Inj	30 minutes Post-Inj	60 minutes Post-Inj, if required					
Gross visual acuity		SE					SE								
IOP	OU	SE	SE	SE ¹	SE ²	SE	SE	SE	SE ¹	SE ²					
Dilated Fundus	OU	SE				OU	SE								
Anterior Chamber Paracentesis, if required ³		SE					SE								

¹ If the pressure is elevated >10 mmHg above pre-injection or above 30 mmHg when measured at 30 minutes post-injection it must be measured again at 60 minutes post-injection.

² If IOP still elevated at 60 min post-injection, repeat at 30 minute intervals until pressure is < 10 mmHg above pre-injection pressure or < 30 mmHg.

³ Perform anterior chamber paracentesis if no retinal perfusion 2 or more minutes after injection.

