8.4.3 Post-injection safety assessments

Post-injection safety assessments are described in [Table 8-3](#) Post-Injection Exams at Injection visits. Within 0-5 minutes after an IVT injection, perfusion of the central retinal artery must be verified by indirect ophthalmoscopy in case of non-perfusion treat with anterior chamber

Novartis

Confidential

Page 70

Amended Protocol Version No. 01 (Clean)

Protocol No. CCLG561X2201A

paracentesis 2 or more minutes after injection. Normalization of intraocular pressure must be verified within 30 minutes of the injection. Intraocular pressure must be re-measured again at 60 minutes post injection if the pressure is elevated > 10 mmHg above the pre-dose value or if the pressure is above 30 mmHg.

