9.3 Procedures for recording and reporting AEs and SAEs

Subsequent to signing an informed consent form, all untoward medical occurrences that occur during the course of the study must be documented on an Adverse Event Form (AEF). A separate AEF must be filled out for each event. When possible, signs and symptoms indicating a common underlying pathology must be documented as one comprehensive event. For each recorded event, the AE documentation must include the onset date, outcome, resolution date (if event is resolved), intensity (e.g., severity), any action with study treatment taken as a result of the event, and an assessment of the AE's relationship to the study

Novartis

Confidential

Page 74

Amended Protocol Version No. 01 (Clean)

Protocol No. CCLG561X2201A

Once an AE is detected, it must be followed until its resolution or until it is judged to be permanent, and assessment must be made at each visit (or more frequently, if necessary) of any changes in severity, the suspected relationship to the study drug, the interventions required to treat it, and the outcome.

Information about common side effects that are already known about the investigational drug can be found in the IB or Core Data Sheet (for marketed drugs) or will be communicated between IB updates in the form of Investigator Notifications. This information will be included in the subject informed consent and must be discussed with the subject during the study as needed.

The Investigator should also instruct each subject to report any new AE (beyond the protocol observation period) that the subject, or the subject's personal physician, believes might reasonably be related to study treatment. This information must be recorded in the Investigator's source documents; however, if the AE meets the criteria of an SAE, it must be reported to Sponsor.

Non-serious Adverse Events

A non-serious AE is defined as any untoward change in a subject's medical health that does not meet serious criteria noted below (e.g., is not life-threatening, does not require hospitalization, does not prolong a current hospitalization, is not disabling, etc.). All AEs must be reported regardless of whether or not they are related to the study treatment. For non-serious AEs, an AEF containing all available information will be collected on a routine basis according to instructions provided by the study sponsor.

Serious Adverse Events

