- Grade 2 aqueous flare and/or Grade 2 or 3 aqueous cells that fail to decrease to 1 or less within 30 days of the onset of the event (see MOP for grading scale)
- Grade ≥ 2 vitreous haze and/or Grade ≥ 3 vitreous cells (see MOP for grading scale)
- ≥ 30 letter decrease in BCVA compared with Baseline visual acuity
- Sustained (> 15 minutes) loss of light perception due to elevated IOP
- IOP > 30 mmHg at/past 60 minutes post injection
- New retinal tear or detachment
- New vitreous hemorrhage $> 2+$ severity that does not resolve within 30 days of the onset of the event (see MOP for grading scale)

If an ESI occurs in a study subject, a decision will be made by the Sponsor concerning further exposure to study treatment. The study subject will be followed for resolution of the ESI and a decision will be made by the Sponsor concerning further participation in the study.

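### Table 8-3 footnote 2 lets the post-injection IOP repeats stop while the eye still meets the protocol's own definition of elevated

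*Protocol*

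**What the plan says.** Three places in the protocol govern IOP checks after an injection.

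- **Table 8-3, footnote 1** sets the trigger for a 60-minute reading: "If the pressure is elevated >10 mmHg above pre-injection or above 30 mmHg when measured at 30 minutes post-injection".
- **Section 8.4.3** gives the same trigger: "if the pressure is elevated > 10 mmHg above the pre-dose value or if the pressure is above 30 mmHg". It contains no stop rule.
- **Table 8-3, footnote 2** covers an eye still elevated at 60 minutes. The site is to "repeat at 30 minute intervals until pressure is < 10 mmHg above pre-injection pressure or < 30 mmHg".

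Footnote 2 does not define elevated itself. The only nearby definition is the trigger in footnote 1, which Section 8.4.3 repeats.

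Two parts of Section 9.3 bear on the consequence. The list of adverse events of special interest includes "IOP > 30 mmHg at/past 60 minutes post injection", and for such events "The study subject will be followed for resolution of the ESI". For adverse events generally, once one is detected, "it must be followed until its resolution or until it is judged to be permanent".

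**The concern.** The trigger and the stop use the same two thresholds, 10 and 30 mmHg, and both join them with *or*. An eye is no longer elevated only when both conditions have cleared, so a stop that needs only one of them is looser than the trigger. Footnote 2 then conflicts with itself for some eyes at 60 minutes: they must enter the repeats because they are still elevated, yet they already meet the condition that ends them.

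Safety is a primary objective (Section 2.1), with treatment-emergent changes in ocular parameters among its endpoints. Section 3.6 lists raised IOP among the risks of every intravitreal injection. Both active arms receive 100 µL at up to 12 visits. In Table 8-2 only the Day 1 and Day 29 injections are followed by a next-day visit (Day 2 and Day 30). After the other ten injections, Day 57 to Day 309, the next scheduled visit is 28 days later, so the same-visit repeats carry more of the load.

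**Working it through.** This is a check of logic, and the protocol states no figure to reproduce. Let *p* be the pre-injection IOP and *v* a later reading, both in mmHg.

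**Rules**

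- Trigger (footnote 1, Section 8.4.3): *v − p* > 10 **or** *v* > 30.
- Stop as written (footnote 2): *v − p* < 10 **or** *v* < 30.
- Logical complement of the trigger: *v − p* ≤ 10 **and** *v* ≤ 30.

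**Worked cases**

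| *p* | *v* | Rise | Elevated? | Stop met as written? | Stop met with complement? |
|---|---|---|---|---|---|
| 14 | 28 | 14 | yes (rise > 10) | yes (*v* < 30) | no |
| 24 | 33 | 9 | yes (*v* > 30) | yes (rise < 10) | no |
| 20 | 30 | 10 | no | no | yes |

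The first two rows are elevated and released together. The third is a boundary gap in the other direction: neither elevated nor released.

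**Timing.** If the stop is tested only from the first repeat at 90 minutes, such an eye gets one further reading. A 90-minute value of 28 (from 14) or 33 (from 24) still ends the repeats.

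**How many value pairs are affected.** Assume whole-mmHg values, *p* from 8 to 25, and *v* from *p* up to some limit of at least 34. The 25 echoes exclusion criterion 15 ("Uncontrolled ocular hypertension or glaucoma in the study eye (IOP > 25 mmHg despite current pharmacological or non-pharmacological treatment"), which applies at entry only and does not bound IOP at later injection visits. The 8 is an assumption.

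- Below 30 mmHg: *v* runs from *p* + 11 to 29, giving 19 − *p* values for *p* = 8 to 18. Sum: 11 + 10 + … + 1 = 66. The extreme is 29 mmHg from a pre-injection value of 8, a rise of 21.
- Above 30 mmHg: *v* runs from 31 to *p* + 9, giving *p* − 21 values for *p* = 22 to 25. Sum: 1 + 2 + 3 + 4 = 10. The highest reading is 34.
- At exactly 30 mmHg: none, because an elevated eye there has a rise above 10 and meets neither stop condition.
- Total: 66 + 10 = 76.
- Neither elevated nor released: one pair, (20, 30).
- With the complement as the stop: 0 pairs elevated and released, 0 pairs neither.

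**What the count depends on.** It does not depend on the upper limit for *v*, but its share of elevated pairs does: 76/258 = 29.5% with a limit of 40, 76/438 = 17.4% with 50, and 76/618 = 12.3% with 60. It also depends on the assumed range of *p*: 10–25 gives 45 + 10 = 55, 12–25 gives 28 + 10 = 38, and 8–30 (with *v* reaching at least 39) gives 66 + 45 = 111. No share or rate is therefore claimed.

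**The case against.** The strongest reply is that a trigger and a stop do different jobs and need not mirror each other. The protocol's level of concern from 60 minutes on is 30 mmHg, as the special-interest list shows, so ending mandatory repeats below 30 could be deliberate. Many of the affected pairs are mild: in 28 of the 66 below 30 mmHg the reading is 25 or less, a level that exclusion criterion 15 would not call uncontrolled. All 10 pairs above 30 mmHg become events of special interest at or past 60 minutes, reportable within 24 hours and followed to resolution. Section 8.4.3 also asks for normalization to be verified within 30 minutes, further ocular examinations and unscheduled visits are at the investigator's discretion, and the manual of procedures, which is not shown, may say more.

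Most of this stands as a limit on the consequence. It does not rescue the wording. A deliberately looser stop would not already be met by eyes that the same footnote sends into the repeats, and it would not release eyes above 30 mmHg, the very level at which the protocol requires special-interest reporting. Next-day IOP checks follow only the first two injections. The pair count adds little beyond showing that such states exist, and it is offered only for that.

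**Conclusion.** The footnote is wrong as written. Its stop is not the complement of the trigger, and nothing else in the protocol corrects it. This rests on reading elevated in footnote 2 by the definition in footnote 1 and Section 8.4.3, the only one available.

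The practical size is limited. Above 30 mmHg, special-interest reporting and follow-up provide a backstop. Below 30 mmHg they do not: footnote 2 sets the same-visit schedule, and anything further, including whether the reading counts as an adverse event, rests mainly on the investigator's judgement. The 76 pairs (66 below 30 mmHg, 10 above) hold for the assumed grid and say nothing about how often patients would be affected. The efficacy analysis, alpha and sample size are untouched. It should be corrected because it concerns safety monitoring under a primary safety objective and the correction is simple.

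**What to change.** Reword the stop in footnote 2 so that repeats continue at 30-minute intervals until the pressure is **≤ 10 mmHg above the pre-injection value and ≤ 30 mmHg**. This removes both the overlap and the boundary gap. If the clinical team prefers other thresholds, the stop should still be the exact complement of the trigger, with the same change made in footnote 1 and Section 8.4.3.

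The cost is one footnote and a few extra IOP readings at some injection visits. One side effect should be accepted knowingly: an eye already above 30 mmHg before an injection would be measured until it fell to 30 or below, even without an injection-related rise. The existing trigger already calls that eye elevated, so the change follows the protocol's own definition.

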8.1 Informed consent procedures

Informed consent must be obtained before conducting any study-specific procedures (i.e. all of the procedures described in the protocol). The process of obtaining informed consent must be documented in the subject source documents.

Eligible subjects are included in the study after providing written (witnessed, where required by law or regulation) IRB/IEC-approved informed consent. If incapable of doing so, in cases where the subject's representative gives consent, the subject will be informed about the study to the extent possible given his/her understanding. If the subject is capable of doing so, he/she should indicate assent by personally signing and dating the written informed consent document or a separate assent form. The date of signing of informed consent (and withdrawal, if later withdrawn) must be documented in the eCRF.

The Sponsor will provide the Investigators with a proposed informed consent form that complies with the ICH GCP guideline and regulatory requirements. Any changes to the proposed informed consent form suggested by the Investigator must be agreed to by Sponsor before submission to the IRB/IEC.

Corporate Confidential Information

A copy of the approved version of all consent forms must be provided to the Sponsor monitor after IRB/IEC approval.

8.2 Subject demographics/other baseline characteristics

Subject demographic and baseline characteristic data is collected on all subjects as stated in the MOP.

Relevant medical history/current medical conditions data includes data until signature of informed consent. When possible, diagnoses (not symptoms) must be recorded. Medical history/current medical conditions are confirmed at Visit 1 prior to drug administration.

Investigators have the discretion to record abnormal test findings that occurred prior to the informed consent signature on the medical history eCRF.

Ocular and AMD History

Past or current ocular history and history of AMD diagnosis, history of GA diagnosis, progression, and treatments must be captured on the appropriate eCRF. Ocular function questions must be reviewed as stated in the CLG561-2201 MOP.

Novartis

Confidential

Page 67

Amended Protocol Version No. 01 (Clean)

Protocol No. CCLG561X2201A

Family History

First degree family history of ocular, renal and cardiovascular diseases must be gathered and captured on the appropriate eCRF as part of the medical history assessment.

Dietary History

Subjects must be asked to estimate their weekly consumption of fish (servings per week) and daily consumption of fruits and vegetables (servings per day). Subjects must be asked whether they use an AREDS-type supplement or omega-3 fatty acid supplement.

Alcohol and Drug Dependence History

All subjects must be asked to provide a verbal history of alcohol and drug dependence (e.g., alcohol, amphetamines, barbiturates, benzodiazepines, cannabinoids, cocaine, opiates, etc.). The Investigator must use good clinical judgment based on the subject's verbal history in regard to the inclusion or exclusion of the subject.

Smoking History

Subjects must be asked to provide smoking history in during screening.

Hepatitis and HIV History

All subjects are screened for history of Hepatitis B, Hepatitis C, and HIV. Screening will be based on a verbal history and confirmed by central lab analysis. Results are available as source data only. In the event of a positive case, the subject must be informed of the result. The Investigator must instruct the subject to seek appropriate medical care and provide physician referrals as necessary.

8.3 Efficacy / pharmacodynamics

Pharmacodynamic assessments are specified below. Assessments are performed and samples and images are collected at the time point(s) defined in the assessment schedule.

8.3.1 Pharmacodynamic sample collection

Concentrations of total C5 concentrations of total properdin, and

Corporate Confidential Information

Corporate Confidential Information

All samples are given a unique sample number as indicated in the log that is included in the MOP. Further details on sample collection, numbering, processing and shipment can be found in the MOP.

8.3.2 Pharmacodynamic analytical methods

Determination of the concentration of total properdin and total C5 in serum is performed using either an immunoassay or Liquid Chromatography – Tandem Mass Spectrometry (LC/MS/MS) method. A detailed description of the methods used to quantify the concentration of total properdin and total C5 is included in the bioanalytical raw data of the study and in the bioanalytical data report. The LLOQ is documented in the bioanalytical data reports.

Novartis

Confidential

Page 68

Amended Protocol Version No. 01 (Clean)

Protocol No. CCLG561X2201A

Corporate Confidential Information

8.3.3 Ocular pharmacodynamic assessments

Corporate Confidential Information

The methods for assessment and recording are specified in the IAG for the sites and in the IRC and Reviewer Training Manual for the CRC.

Certification of the equipment and examiners at each investigative site will occur prior to the evaluation of study subjects. The methods for assessment and recording are specified in the IAG for the sites and in the IRC and Reviewer Training Manual for the CRC.

8.3.3.2 Fluorescein angiography (FA)

FA is performed using a standardized technique. FA is performed for each subject according to the assessment schedule. The methods for assessment and recording are specified in the IAG for the sites and in the IRC and Reviewer Training Manual for the CRC.

Certification of the equipment and examiners at each investigative site will occur prior to evaluation of study subjects.

8.3.3.3 Fundus autofluorescence (FAF)

FAF is performed on each subject according to the assessment schedule. The methods for assessment and recording are specified in the IAG for the sites and in the IRC and Reviewer Training Manual for the CRC.

Certification of the equipment and examiners at each investigative site will occur prior to evaluation of study subjects.

8.3.3.4 Color fundus photography (CFP)

CFP will be performed on each subject according to the assessment schedule. The methods for assessment and recording are specified in the IAG for the sites and in the IRC and Reviewer Training Manual for the CRC.

Certification of the equipment and examiners at each investigative site will occur prior to evaluation of study subjects. Color fundus photography is undertaken for assessment of safety if needed. The sponsor may request reading of the color fundus photos if needed or may not assess these if not needed.

8.4 Safety

Safety assessments are specified below; methods for assessment and recording are specified in the MOP, with the assessment schedule detailing when each assessment is performed.

8.4.1 Vital signs and body measurements

Vital signs measured include:

- Body temperature
- BP
- Pulse Rate

Body measurements include:

- Height
- Body weight
- BMI will be calculated (Body weight (kg) / [Height (m)]²)

8.4.2 Laboratory evaluations

Clinically relevant deviations of laboratory test results occurring during or at completion of the study must be reported and discussed with Sponsor personnel. The results must be evaluated for criteria defining an AE and reported if the criteria are met. Repeated evaluations are mandatory until normalization of the result(s) or until the change is no longer clinically relevant. In case of doubt, Sponsor personnel must be contacted.

Hematology

Hemoglobin, hematocrit, red blood cell count, white blood cell count with differential and platelet count are measured.

Clinical chemistry/blood chemistry

Sodium, potassium, creatinine, urea, uric acid, chloride, albumin, calcium, alkaline phosphatase, total bilirubin, LDH, GGT, AST, ALT, aPTT, PT/INR, CK, glucose, total cholesterol, triglycerides. If the total bilirubin concentration is increased above 1.5 times the upper limit of normal, direct and indirect reacting bilirubin is differentiated.

Urinalysis

Urine test by dipstick: leucocytes, nitrite, pH, protein, glucose, ketones, urobilinogen, bilirubin, blood/ hemoglobin.

If the dipstick result is positive for protein, nitrite, leucocytes and/or blood, the sample must be sent for microscopic analysis of WBC, RBC and casts.

8.4.3 Post-injection safety assessments

Post-injection safety assessments are described in [Table 8-3](#) Post-Injection Exams at Injection visits. Within 0-5 minutes after an IVT injection, perfusion of the central retinal artery must be verified by indirect ophthalmoscopy in case of non-perfusion treat with anterior chamber

Novartis

Confidential

Page 70

Amended Protocol Version No. 01 (Clean)

Protocol No. CCLG561X2201A

paracentesis 2 or more minutes after injection. Normalization of intraocular pressure must be verified within 30 minutes of the injection. Intraocular pressure must be re-measured again at 60 minutes post injection if the pressure is elevated > 10 mmHg above the pre-dose value or if the pressure is above 30 mmHg.

